OHRP	Office for Human Research Protections
OHSR	Office of Human Subjects Research
PI	Principal Investigator
QA	Quality Assurance
QC	Quality Control
SAE	Serious Adverse Event/Serious Adverse Experience
SOP	Standard Operating Procedure
US	United States

CONFIDENTIAL

This material is the property of the NYU School of Medicine and Langone Medical Center. Do not disclose or use except as authorized in writing by the study sponsor
Interventional Template Version: 28 APR 2017

[figure not shown]
Protocol Summary

Title	The Efficacy of Retapamulin as a Topical Decolonizing Agent for Mupirocin-Resistant Methicillin-Resistant Staphylococcus aureus (MRSA)
Short Title	Retapamulin as a Decolonizing Agent for MRSA
Brief Summary	A randomized, double-blind, placebo-controlled clinical trial to test the efficacy of retapamulin to decolonize MRSA in a high risk pediatric group aged 9 months-17 years. The sample size will include 27 subjects in each of the two arms of the study (retapamulin versus placebo) for a total of 54 subjects. Participants who are found to be nasal and/or rectal colonized with MRSA will be randomized to receive either retapamulin or placebo applied nasally and rectally for a total of 5 days. Nasal and rectal swabs will be collected at pre-defined time points during study duration (screening swab, swab one week after completion of topical therapy, swab 4 weeks after completion of topical therapy) to assess MRSA colonization status. The colonization rates of both groups will be assessed via Fisher's Exact Test.
Phase	Clinical study phase 3
Objectives	To investigate the efficacy of retapamulin to reduce carriage of MRSA via a randomized, double-blind, placebo-controlled clinical study testing retapamulin among patients with confirmed mupirocin-resistant nasal and/or rectal MRSA colonization.
Methodology	Randomized, double-blind, placebo-controlled clinical trial
Endpoint	Primary Endpoint: Nasal/Rectal MRSA carriage at 1 week following decolonization course Secondary Endpoint: Nasal/Rectal MRSA carriage at 4 weeks following decolonization course
Study Duration	2 years
Participant Duration	6 weeks
Duration of IP administration	5 days
Population	27 patients per the two arms of the study aged 9 months-17 years for a total of 54 participants, of both genders. Patients are required to be colonized with a mupirocin-resistant methicillin-resistant strain of Staphylococcus aureus of which there is currently an outbreak in a particular high risk geographical cluster (children living in Brooklyn NY of Orthodox Jewish descent). The patients will be sampled from admitted children who reside in Orthodox predominant neighborhoods in Brooklyn NY based on zip code of residence.
Study Sites	NYU Langone Medical Center - Tisch Hospital, ODA clinic in Brooklyn
Number of participants	54 participants across both arms of the study
Description of Study Agent/Procedure	Retapamulin is a topical antibiotic ointment. The study drug (and placebo) will be used topically in a thin layer to the nares and peri-rectal area twice a day for five consecutive days
Reference Therapy	Placebo (white petrolatum)
Key Procedures	Body surface swabs/cultures
Statistical Analysis	Statistical analysis will be performed using Fisher's exact test (non-parametric) to evaluate for significant difference in colonization between the two groups (retapamulin and placebo).

CONFIDENTIAL

This material is the property of the NYU School of Medicine and Langone Medical Center. Do not disclose or use except as authorized in writing by the study sponsor
Interventional Template Version: 05 JAN 2017

Schematic of Study Design

CONFIDENTIAL

This material is the property of the NYU School of Medicine and Langone Medical Center. Do not disclose or use except as authorized in writing by the study sponsor
Interventional Template Version: 28 APR 2017

1 Key Roles

Principal Investigator

[name] [name]: Hospital Epidemiologist, Assistant Professor of Pediatric Infectious Diseases
NYU School of Medicine
[name]
[contact]
[contact]

Co-investigator

[name], MPH: Pediatric Infectious Diseases Fellow
NYU School of Medicine
[name]
[contact]
[contact]

Industry Partner/Industry Sponsor

Aqua Pharmaceuticals
[name], DMD: Senior Director of Clinical and Medical Affairs
[name]: VP of Research and Development
[name]
[name]
[contact]

Biostatistician

[name], CIC: Data Analyst
NYU Langone Medical Center
[name]
[contact]
[contact]

Research Coordinator

2.1 Background Information and Relevant Literature

Staphylococcus aureus (*S. aureus*) is a leading cause of superficial and invasive hospital and community-acquired infections. It is the most virulent of the *Staphylococcus* species and can produce systemic infections in otherwise healthy adults and children. The anterior nares are a natural reservoir for *S. aureus*, and colonization confers an increased risk of infection.^[1] National data indicate that the prevalence of asymptomatic colonization with methicillin-sensitive *S. aureus* ranges from 18 to 38%, and with methicillin-resistant *S. aureus* (MRSA) from 0.8 to 6%.^[1] Controlling MRSA colonization and preventing its spread is essential, as infection is associated with significant morbidity and mortality. Decolonization is an evidence-based intervention that can be used to reduce bacterial burden in order to prevent MRSA infections and transmission.^[2] Standard decolonization regimens include mupirocin ointment to the nares and chlorhexidine wipes or baths for the body. Mupirocin is a topical antibacterial agent that is well established in clinical practice and is currently the gold standard therapy for MRSA nasal decolonization.^[1] However, increasing resistance to mupirocin has been noted with some studies showing that MRSA mupirocin resistance (Mup-R) rates are as high as 24% in the US.^[3] Emerging resistance to mupirocin highlights an urgent need for alternative approaches to MRSA decolonization.

In New York City (NYC), there is a high prevalence of MRSA infections. Over the past several years, pediatric clinicians at New York University Langone Medical Center (NYULMC) have observed an increased incidence of MRSA infections amongst the pediatric population, specifically among Orthodox Jewish children. These observations were confirmed in a 2015 prospective study conducted at NYULMC to better understand the epidemiology of Community Acquired MRSA (CA-MRSA) in the pediatric population. Children from the Orthodox Jewish community were identified as high risk compared to the general pediatric population. Children from the high-risk communities were identified via zip codes as described in a publication that determined Orthodox Jewish neighborhoods based on the concentration of Jewish establishments such as synagogues, yeshivas, and kosher food retailers.^[12] Information was collected to ascertain MRSA infection and colonization rates among these two groups.

CONFIDENTIAL

This material is the property of the NYU School of Medicine and Langone Medical Center. Do not disclose or use except as authorized in writing by the study sponsor
Interventional Template Version: 28 APR 2017

Interestingly, no difference in methicillin-susceptible *S. aureus* (MSSA) colonization prevalence was observed between children from high-risk and low-risk communities. However, children from these high-risk areas were 2.8 times as likely to be colonized with MRSA (prevalence 9% vs 3% [p=0.04]). Likewise, the MRSA infection rate per 1,000 patient days was 36 for children from high-risk areas versus 3.9 in children from low-risk areas (p<0.0001). All isolates from patients in high-risk zip codes analyzed to date belong to genotype USA300, the predominant CA-MRSA clone in the US. This data suggests there is a geographically defined outbreak of CA-MRSA in children and these isolates form a distinct clade within the common USA300 MRSA lineage.

Moreover, the majority of the clinical strains from the outbreak cluster carry the plasmid encoding the *mupA* gene, which confers the mupirocin-resistant (Mup-R) phenotype. Phenotypic analysis confirmed mupirocin resistance in 84% (39/55) of the outbreak subclone isolates compared to none (0/17) in the USA300 CA-MRSA control isolates. This finding has significant clinical impact, as there are no validated approaches to decolonize these children and families, and many such patients are re-hospitalized with recurrent infections. In addition, CA-MRSA transmission in the community is ongoing and transmissions have been observed at our institution. Without an adequate way to decolonize Mup-R MRSA-positive patients, we risk expansion of the outbreak strain to lower risk patients and to communities outside the high risk geographic area.

Retapamulin is a novel topical bacteriostatic pleuromutilin antibiotic, currently used for the treatment of impetigo, which has been shown to be effective against *S. aureus* skin infections. It has excellent in vitro and in vivo activity against MRSA and methicillin-sensitive *S. aureus* (MSSA) strains. An in vitro study to determine the activity of retapamulin among 403 MRSA isolates found that 99% of the MRSA isolates were susceptible to retapamulin.^[4] In a multicenter Global Surveillance Program, *S. aureus* isolates were collected from skin and soft tissue infections of adults and children in hospital and community settings. Among MRSA isolates, retapamulin was 128-fold more potent than mupirocin.^[5]

Multiple in vitro studies have demonstrated that the likelihood of *S. aureus* developing resistance to retapamulin is low. This is in large part due to the antibiotic's mechanism of action, inhibition of bacterial protein synthesis by binding to and preventing formation of the 50S ribosomal unit. A multi-center study was performed by Biedenbach in outpatient dermatology centers to determine the rates of resistance of agents against *S. aureus* isolates collected from skin and soft tissue infections. The rate of mupirocin resistant *S. aureus* isolates was >10%, whereas retapamulin resistance was infrequent (1%).^[5] Reduced susceptibility to retapamulin can occur via mutations in the *cfr* and *rplC* genes.^[6, 7] The *cfr* (chloramphenicol-florfenicol resistance) gene encodes an rRNA methylase. The presence of this gene may lead to enhanced methylation, which is thought to prevent the antimicrobial from binding to the ribosome.^[8] For the *rplC* (ribosomal protein L3) gene, the mechanism of resistance has been identified as first-, second-, and third- step *rplC* mutants of *S. aureus*.^[9] The *rplC* gene encodes the L3 ribosomal protein which is essential for the formation of the peptidyl transferase center, the site where retapamulin binds. Three mutations are needed to have a notable effect; however each mutation confers a considerable fitness cost to the organism, leading to a low probability for the emergence of resistance in *S. aureus*.^[10]

Evidence for retapamulin as an effective decolonizing agent against MRSA is sparse, with even more limited studies in the pediatric population. There is high prevalence of MRSA in New York City, specifically in a geographically defined outbreak of CA-MRSA in children that has resistance to mupirocin, the standard of nasal decolonization. This represents a unique opportunity to gain further insight into retapamulin susceptibility and its efficacy as an alternative decolonizing agent. We hypothesize that retapamulin will be an effective agent to decolonize children harboring mupirocin-resistant MRSA strain.

2.2 Name and Description of the Investigational Agent

Retapamulin is a topical 1% antibiotic ointment that consists of retapamulin and white petrolatum as the vehicle. Retapamulin is a white to pale yellow crystalline solid. It is a bacteriostatic pleuromutilin antibiotic which inhibits bacterial protein synthesis by binding to and preventing formation of the 50S ribosomal unit.

CONFIDENTIAL

This material is the property of the NYU School of Medicine and Langone Medical Center. Do not disclose or use except as authorized in writing by the study sponsor
Interventional Template Version: 28 APR 2017

The recommended dose is a thin layer of ointment applied twice a day for five days. Systemic exposure following application to intact skin is generally very low.

It was FDA approved in 2007 for topical use in patients over 9 months of age. It is indicated for impetigo and mild secondary skin infections arising from lacerations, abrasions, sutured wounds, psoriasis or dermatitis. These infections are mainly caused by *Staphylococcus aureus*, but can also be due to *Streptococcus pyogenes*.

The drug meets IND exemption criteria as it meets all 6 criteria for IND Exemption in article 312.2(b) of the FDA Guidance and IND requirements. Please see attached IND appendix.

2.2.1 Preclinical Data

The study drug, retapamulin, was tested in the [name] laboratory at NYU by the study team to assess susceptibility to the isolates of the strain in question. The initial epidemiologic study in 2015-2016 conducted by [name] and [name], PhD described the outbreak of MRSA in this geographically defined high risk pediatric population. The genotypic and phenotypic analyses demonstrated that this MRSA strain is a subclone of the common USA 300 lineage and carries the *mupA* gene which confers resistance to mupirocin.

The isolates from the subjects in the above study were tested via broth dilution to determine minimum inhibitory concentration (MIC) of retapamulin to assess susceptibility. This in vitro data shows that all of these isolates are susceptible to the study drug, retapamulin.

2.2.2 Clinical Data to Date

Multiple in vitro and in vivo studies have been published to date that have demonstrated retapamulin activity against MRSA (a few referenced above in the background and listed in the reference section). Studies have tested retapamulin in vitro to determine susceptibility and MIC data and have found the drug to be effective against MRSA isolates. These studies have also compared these isolates to mupirocin, the standard of care in decolonization, to compare efficacy with retapamulin which was shown to be very efficacious.

A recent abstract/poster was presented at the Infectious Diseases Society of America (IDSA) 2016 ID week. The study was a randomized double-blinded placebo-controlled trial to assess effect of retapamulin for nasal decolonization of mupirocin-resistant MRSA nasal carriers. This trial found that nasal retapamulin reduced MRSA nasal carriage at 1 week following application of the study drug (84% reduction in odds of MRSA carriage compared to placebo) but reductions were not sustained at 6 weeks. This study found retapamulin was well tolerated when applied nasally with no reported side effects.^[18]

2.2.3 Dose Rationale (if applicable)

The recommended dose for retapamulin is a thin layer of ointment applied twice a day for five days. This type of dosing is common for MRSA decolonization protocols and guidelines with other topical ointments.

2.3 Rationale

Methicillin resistant *Staphylococcus aureus* (MRSA) is a significant pathogen that causes a wide spectrum of superficial and invasive hospital and community-acquired infections. Controlling MRSA colonization is essential to prevent infections and transmission of the pathogen. At NYU Langone Medical Center there is a high prevalence of MRSA infections, specifically within a geographically defined community. Genotypic and phenotypic analysis of isolates from these patients demonstrates that the majority are resistant to mupirocin, the standard of care for decolonization. There is limited evidence of other alternative topical decolonizing strategies. In this study we will investigate the efficacy of decolonization in this pediatric population with a novel topical antibiotic, retapamulin which has been shown in a limited number of previous studies to be effective against MRSA.

CONFIDENTIAL

This material is the property of the NYU School of Medicine and Langone Medical Center. Do not disclose or use except as authorized in writing by the study sponsor
Interventional Template Version: 28 APR 2017

Study Aim:

To investigate the efficacy of retapamulin to reduce carriage of MRSA via a randomized, double-blind, placebo-controlled clinical trial testing retapamulin among pediatric patients with confirmed mupirocin-resistant nasal and/or rectal MRSA colonization.

Hypothesis:

Retapamulin will be an effective way to decolonize children harboring mupirocin-resistant CA-MRSA strain compared to placebo at 1 week and 4 weeks post treatment. Specifically, we hypothesize retapamulin will reduce MRSA carriage by 60%.

2.4 Potential Risks & Benefits

2.4.1 Known Potential Risks

Known risks or adverse reactions from this drug use are minimal and include local application site irritation (pruritus, erythema, stinging). In clinical studies, this was found to occur in less than 2% of patients. Retapamulin has not yet been widely evaluated for use on mucosal surfaces. This information is listed in the package insert for retapamulin.

We do not anticipate that this research study will pose greater than minimal risk to participants. Side effects of Retapamulin not commonly expected and should subside with the discontinuation of the drug without expected long term risks. Serious side effects are rare and can include allergic reaction.

All efforts will be made to minimize risk for participants in this study. Study staff have been trained in human subjects' research and protection. The subjects will be instructed on proper use (amount, technique, duration) of the study drugs and potential effects to monitor for. If a side effect were to occur or there are any concerns, the subjects will be advised to call the research staff immediately and guidance or treatment will be offered as needed. Immediate necessary care for adverse events will be provided at NYULMC. Subjects will be monitored for side effects at each study visit and check-in via telephone to parent/guardian. If subjects experience serious adverse events or side effects to the study drug they will be withdrawn from the study.

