5.7.2 Handling of Participant Withdrawals or Termination

For patients who have withdrawn or terminated from the study, follow up telephone calls will be conducted to assess for side effects. One phone call two weeks after the patient has been declared

CONFIDENTIAL

This material is the property of the NYU School of Medicine and Langone Medical Center. Do not disclose or use except as authorized in writing by the study sponsor
Interventional Template Version: 28 APR 2017

withdrawn or terminated will be conducted. For patients who remain in the study, but discontinue the study agent, they will be asked to complete the follow up questionnaire when they present for study visits to assess for adverse reactions or side effects. Adverse events from the drug are local at the site of application and should subside with the discontinuation of the product. Therefore, long term follow up for adverse events is deemed unnecessary.

A participant will be stated as lost to follow-up (and therefore withdrawn/terminated) if: they have missed all three study visits, the study team has attempted weekly phone calls to parent/guardian for three weeks without answer or success of having the participant return for study visit.

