10.3 Analysis Datasets

This will be a triple-blinded randomized Intent to Treat (ITT) clinical trial to assess the effectiveness of retapamulin in children colonized with MRSA under the age of 18 from a pre-specified community in Brooklyn. Participants living in the following zip codes will be eligible: 11024, 11205, 11206, 11211, 11213, 11214, 11218, 11219, 11225, 11230, 11249. Neither the treatment team nor the subject will know the treatment assignments. The outcome will be a dichotomous variable (1 = Yes, patient's swab negative for MRSA, 0 = No, Patient's swab positive for MRSA). We will analyze additional co-variables collected on the data collection form such as age, gender, history of MRSA infections, history of chronic medical conditions/chronic skin conditions, etc. (see Data Collection Form in appendix uploaded into study-related documents).

Information from the data collection form will be entered into an Access database designed for this study to provide a readily electronic version dataset to analyze. The following variables will be included: Assigned group (blinded treatment arm, A/B), age, gender, side effects, application day 1 (Y/N), application day 2 (Y/N), application day 3 (Y/N), application day 4 (Y/N), application day 5 (Y/N), environmental clean (Y/N), history of medical conditions or chronic skin conditions, history of MRSA, history of MRSA in family, recent or concomitant antibiotic use, prior retapamulin use etc. Variables related to safety will also be recorded in the database.

In addition to the ITT analysis, we will conduct a per-protocol analysis of those who completed 4 or 5 days of treatment and analyze similar to the ITT analysis.

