10.5 Sample Size

The table below presents ranges of the required sample size based on the primary trial endpoint of the change in nasal/rectal colonization of MRSA from baseline to 1 week after completion of decolonization protocol at approximately 80% power. It provides a range of sample size depending on the potential effectiveness of retapamulin.

Computed N Per Group		
Proportion Diff	Actual Power	N Per Group
0.30	0.809	42
0.35	0.801	32
0.40	0.807	26
0.45	0.822	22
0.50	0.811	18
0.55	0.802	15
0.60	0.808	13
0.65	0.841	12

The sample size calculation was based on prior literature indicating a 60% decolonization rate; a 45% difference in decolonization between groups (60% retapamulin vs 15% placebo/spontaneous decolonization) at 80% power. This is taken into account a 15% spontaneous decolonization rate as reported in the literature. Power calculation analyses were performed in SAS 9.3 (SAS Institute, Cary NC) using fisher's exact conditional test for two proportions (Walters normal approximation with exact conditional distribution). A 20% lost to follow up was estimated and added to the final sample size number. Therefore, the total number of participants enrolled will be 54 subjects – 27 in each of the two arms of the study.

It is estimated that 0.8-6% of the general population is colonized with MRSA. Colonization in persons with previous infection is estimated to be 20%. We suspect this percent is higher in the particular population we aim to study as it is a high risk population for MRSA colonization and infection. Therefore we estimate screening 500 participants to meet the sample size goal of our study.

CONFIDENTIAL

This material is the property of the NYU School of Medicine and Langone Medical Center. Do not disclose or use except as authorized in writing by the study sponsor

We will use fisher exact test at alpha .05 to determine a significant difference between treatment groups (retapamulin vs placebo). Participants who withdraw before the 1 week primary endpoint will be excluded from analysis as the primary end point will not be recorded.

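### Section 2.4.1 withdraws children with drug reactions from the study, not just from the drug, so section 10.5 can drop them from a primary analysis that section 10.3 calls ITT

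*Combined protocol and SAP*

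**What the plan says.** - **Withdrawal rule (2.4.1).** "If subjects experience serious adverse events or side effects to the study drug they will be withdrawn from the study". The wording is mandatory and refers to the study. The same paragraph says of an ordinary side effect or worry that "guidance or treatment will be offered as needed", and the paragraph before it says "Serious side effects are rare and can include allergic reaction".
- **Looser statements elsewhere.** Section 5.7.1 lets the investigator end participation but does not require it. Section 5.7.2 recognises children who stop the ointment and stay: "For patients who remain in the study, but discontinue the study agent, they will be asked to complete the follow up questionnaire". Section 10.4.5 stops only the intervention after a serious side effect such as anaphylaxis.
- **After withdrawal.** Section 5.7.2: "For patients who have withdrawn or terminated from the study, follow up telephone calls will be conducted to assess for side effects". Section 7.3.5 attempts one swab at the time of withdrawal and gives it no role in the primary analysis.
- **Analysis.** Section 10.5: "Participants who withdraw before the 1 week primary endpoint will be excluded from analysis as the primary end point will not be recorded". Section 10.3 calls the trial ITT and continues: "In addition to the ITT analysis, we will conduct a per-protocol analysis of those who completed 4 or 5 days of treatment".
- **Timing.** Five consecutive days of ointment (6.1.9); Visit 2 at Day 14 +/- 5 (7.3.3.1).

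**The concern.** Stopping a drug and leaving a study are different events. Under ITT a child who stops early is still followed and counted in the randomised arm. Section 10.3 implies this, because its per-protocol set of children with 4 or 5 days of treatment has a purpose only if children with fewer days are in the ITT set. Section 2.4.1 can take those same children out of the study, and section 10.5 then takes them out of the analysis.

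The loss occurs after randomisation and is caused by a reaction to the assigned ointment. If a child who stops early is less likely to be cleared (an assumption; the documents do not say), dropping that child raises the apparent clearance rate on retapamulin.

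**Working it through.** **1. The plan's own figure.** Inputs from section 10.5: 60% versus 15% clearance, Fisher's exact test, alpha 0.05, 22 evaluable children per arm. The Walters approximation, two-sided, gives power 0.8216 against the stated 0.822, and all eight table rows match. Exact enumeration gives 0.827. The sample size is therefore not in question; the check below uses the same test and rates at the enrolled 27 per arm.

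**2. Does the withdrawal come before the primary swab?** Visit 2 opens at Day 14 - 5 = Day 9. Ointment is dispensed on Day 0 for five days. A child withdrawn during dosing leaves before the window opens. A child whose event is first reported at Visit 2 is swabbed there and is unaffected.

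**3. How many children?** With rate q per child, the expected number is 27q and P(at least one) = 1 - (1 - q)^27.

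| Reading | q | Expected of 27 | P(at least one) |
|---|---|---|---|
| Serious events only | 0.1% (assumed) | 0.027 | 2.7% |
| Serious events only | 1% (assumed) | 0.27 | 24% |
| Any side effect | 2% (ceiling of the irritation rate in 2.4.1) | 0.54 | 42% |

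The documents give no rate for serious effects beyond calling them rare, so the first two rows are an assumed range.

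**4. How often would it change the result?** Count a flip when Fisher's test (two-sided, 0.05) is not significant with all 27 per arm but is significant in favour of retapamulin once withdrawn children are dropped. Withdrawals are binomial, there is no other loss, and all outcomes are enumerated. The 45% versus 15% column is the 0.30 difference in the section 10.5 table.

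| Scenario | 60% vs 15% | 45% vs 15% |
|---|---|---|
| Retapamulin only, q = 0.1%, all uncleared | 0.12% | 0.30% |
| Retapamulin only, q = 1%, all uncleared | 1.13% | 2.80% |
| Retapamulin only, q = 2%, all uncleared | 2.17% | 5.16% |
| Retapamulin only, q = 2%, clearing at the arm rate | 0.75% | 2.58% |
| Both arms, q = 2%, all uncleared | 1.58% | 3.49% |

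The both-arms row is relevant because the placebo is the same petrolatum vehicle.

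**5. No drug effect (15% in both arms).** With withdrawals on retapamulin only and all uncleared, the flip chance is 0.02%, 0.23% and 0.44% at q = 0.1%, 1% and 2%. With a fixed number of uncleared retapamulin children dropped, the exact type I error goes from 0.014 (none) to 0.035 (two) and 0.040 (five), still below 0.05.

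**6. One child at the planned effect.** 16/27 versus 4/27: difference 59.3% - 14.8% = 44.4 points, p = 0.0016. Drop one uncleared retapamulin child, 16/26 versus 4/27: 61.5% - 14.8% = 46.7 points, p = 0.0006.

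**The case against.** - **Section 2.4.1 is a risk narrative, and section 5.7 governs withdrawal.** Section 5.7 already has the pathway asked for: optional termination, and children who stop the agent yet attend visits, where section 7.1.1 takes swabs. Section 8.1 also speaks of withdrawing the agent. Section 2.4.1 may simply be loose wording for stopping the drug. That is plausible, but nothing says which section prevails, and staff who follow 2.4.1 literally would lose the outcome.
- **It depends on a larger problem.** The harm needs the section 10.5 exclusion, which conflicts with ITT for the whole expected loss: 0.20 x 27 = 5.4 children per arm. Correcting 10.5 for everyone would bring these children back into the analysis. This is true. What would remain is a missing swab that the protocol itself ordered.
- **The rates may be too high.** Section 2.2.2 reports that an earlier placebo-controlled trial of nasal retapamulin found no side effects. This points to the low end, although that trial's size is not given and it covered nasal application only.
- **Flips are not all bias.** With withdrawn children clearing at the arm rate there is still a 0.75% or 2.58% chance, which reflects the discreteness of Fisher's test. Where the drug works, a flip is also a correct rejection. Both points stand; the no-effect figures in step 5 are the fairer guide to false positives, and they are very small.
- **The full SAP is a separate document (10.1).** It may define the ITT set more closely. It would still have to reconcile sections 2.4.1 and 10.5 as written.

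**Conclusion.** The concern holds, as a minor point. Section 2.4.1 orders study withdrawal after a drug reaction, section 10.5 excludes the child if this happens before the 1-week result, and section 10.3 says the analysis is ITT. The looser sections do not cancel 2.4.1.

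Fewer than one affected child is expected on retapamulin under either reading, and the conclusion would change only in a borderline result. The size rests on the assumed 0.1% to 1% for serious events, on 2% as a ceiling for irritation, and on the worst case that withdrawn children are uncleared. Confidence is medium, because the trigger in 2.4.1 can be read two ways and its intent may have been only to stop the ointment.

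**What to change.** 1. Reword section 2.4.1 so that these children stop the study drug and remain in the study, in line with sections 5.7.2 and 10.4.5. When to stop the drug stays a clinical decision for the investigator.
2. Collect their Visit 2 and Visit 3 swabs unless consent is withdrawn.
3. Amend section 10.5 so that they are analysed in their randomised arm.
4. State that the sentence in section 6.1.9 tying evaluability to five days of ointment does not remove them from the ITT set. Without this, rewording 2.4.1 alone could still leave them out.

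The cost is protocol wording only: the swabs are already scheduled for every child (7.1.1 and section 20). Keeping these children also preserves the later examinations of the application sites in those who reacted. The change does not settle how section 10.5 treats the expected 20% loss, which needs its own rule for missing swabs.
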